**Table 2: eDiary Analysis Endpoints**

eDiary Week Ending	Trial Time
Baseline	The 28 days starting from the first eDiary entry
Weeks 1- 4	Days: 1-28
Weeks 5- 8	Days: 29-56
Weeks 9- 12	Days: 57-84
Weeks 13-16	Days: 85-112
Weeks 17-20	Days: 113-140
Weeks 21-24	Days: 141-168
Weeks 25-28	Days: 169-196
Weeks 29-32	Days: 197-224
Weeks 33-36	Days: 225-252
Weeks 37-40	Days: 253-280
Weeks 41-44	Days: 281-308
Weeks 45-48	Days: 309-336

#### 4.1. Sample Size

Approximately 400 patients (200 per arm) are required to provide 90% statistical power to detect an expected treatment difference of 16%. This calculation assumes a topiramate responder rate of 28% and a BOTOX responder rate of 44% at the primary timepoint of Week 32. A responder is defined as having a  $\geq 50\%$  decrease from baseline in the frequency of headache days per 28-day period. The above calculations were based on a 2-sided test at  $\alpha = 0.05$ , using the commercial software nQuery Advisor version 6.01, procedure PTT1 for a two-group continuity corrected Chi-squared test of equal proportions, with equal sample sizes.

The assumed responder rate for BOTOX was estimated from 2 Allergan Phase 3 double-blind, placebo-controlled studies which reported observed rates of 43.5% (113/260), 50.5% (141/279), and 47.1% (254/539) for Study 191622-079, Study 191622-080, and their pooled/combined data, respectively, at the primary timepoint of Week 24 (Aurora et al, 2010; Diener et al, 2010). At Week 32, the observed rates were 55.7% (141/253), 61.7% (161/261), and 58.8% (302/514), respectively. The corresponding rates for the Intent-To-Treat (ITT) analysis where patients who terminated from the study were treated as failures were reported as 41.3% (141/341), 46.4% (161/347), and 43.9% (302/688), respectively. Based on these 2 studies, the BOTOX responder rate for an ITT analysis at Week 32 ranged from 41.3% to 46.4%, and the value of 44% was chosen as reasonable for the purposes of sample size calculation for the current study.

The topiramate responder rate was estimated from 2 published articles. A double-blind, placebo-controlled study with combination therapies, topiramate + placebo (n = 95) and topiramate + propranolol (n = 96) is described in Silberstein et al, 2012. The observed responder rates for  $\geq 50\%$  decrease in headache days from baseline reported at Week 24 were 28% (23/82) and 31% (26/84), respectively, for the 2 treatment groups. These rates correspond to 24% and 27%, respectively, for an ITT analysis where patients who terminate from the study are treated as failures. Rothrock et al, 2005 also describes an open-label study involving topiramate (n = 170), where a responder rate ( $\geq 50\%$  reduction from baseline) of 38.8% (45/116) was reported. This rate corresponds to 29.4% for an ITT analysis where patients who terminate from the study are treated as failures. Thus, the ITT responder rate for topiramate ranged from 24% to 29.4%, and the value of 28% was deemed reasonable for sample size calculation purposes.

## **4.2. Randomization, Stratification, and Blinding**

On Day 1, qualified patients will be randomly assigned at a 1:1 treatment allocation ratio to 1 of 2 treatment arms: 155 U BOTOX given IM or up to 100 mg/day of oral topiramate.

Randomization is not stratified for this study.

At the screening visit, once informed consent is obtained, the site staff will log onto the interactive web response system (IWRS) to obtain a unique patient number, which will be used as identification for the electronic patient eDiary, electronic case report form (eCRF), electronic clinical outcomes assessments (eCOA), and all source documentation throughout the study.

The IWRS system will provide the site with the treatment assignment to which the patient is assigned. Sites will dispense study medication according to the IWRS instructions. Sites will log onto the IWRS at subsequent visits to log dispensing of additional study medication as needed. Sites will receive the IWRS confirmation notifications for each transaction. All notifications are to be maintained with the study source documents.

## **4.3. Analysis Sets**

### **4.3.1. Intent-to-Treat**

The ITT Set will include all randomized patients.

### **4.3.2. Subset of ITT**

A subset of the ITT Set (ssITT) will exclude patients who discontinue treatment for any reason other than the following: AE, lost to follow-up, lack of efficacy, C-SSRS response of “yes” to questions 4 or 5 in the suicidal ideation section or “yes” to any question in the suicidal behavior section, or noncompliance with the study treatment regimen.

ssITT set analyses will be performed only as needed which will be determined when number of subjects in this population will be known.

#### **4.3.3. Per Protocol**

The Per Protocol (PP) Set will be a subset of patients in the ssITT Set who complete the study without major protocol deviations. Major protocol deviations include one or more of the following categories: major inclusion/exclusion criteria violations, poor study drug compliance, and other. The prespecified criteria for exclusion from the per protocol set are detailed in Section 115.1, and will be finalized prior to the database lock following the completion of the final post-treatment follow-up visit.

PP set analyses will be performed only as needed which will be determined when number of subjects in this population will be known.

#### **4.3.4. Safety**

The Safety Set will include all patients who received at least one dose of study drug.

## **5. Patient Disposition**

Patient disposition will be summarized for all enrolled patients and will include the number and percentage of patients for the following categories: patients randomized, patients treated (Safety Set), patients in the ITT Set, patients in the ssITT Set, patients in the PP Set, patients completed (study treatment and study), patients who discontinued study treatment (including patients who discontinued from topiramate and switched to BOTOX), and patients who discontinued from the study. Denominators for percentages will be the total number of patients randomized into each treatment arm, and overall.

The reasons for study treatment discontinuation and study discontinuation will also be summarized in this table. The reasons for treatment discontinuation may include any of the following: AE, death, lost to follow-up, withdrawal of consent, patient became pregnant, includes non-compliant with study treatment regimen, treatment was ineffective, treatment was no longer needed, existed study due to C-SSRS or other. The reasons for discontinuation will be counted in the treatment arm for which the patient was receiving treatment at the time of discontinuation. These treatment arms will include BOTOX, topiramate, and topiramate + BOTOX.

All patient disposition data will be presented in a listing

### **5.1. Protocol Deviations**

Protocol deviations will be documented by the clinical trial manager and reviewed monthly. They will be categorized as major and minor, and major deviations that would exclude patients from the PP analysis set will be identified and finalized prior to database lock in accordance with International Council for Harmonisation guideline -E9 (Statistical Principles for Clinical Trials). Major protocol deviations include but are not limited to:

- Violation of any inclusion/exclusion criteria
- Poor study drug compliance
- Other protocol deviations as defined by clinical review

Major protocol deviations will be summarized for the ITT Set. Patients will be counted in the treatment arm to which they were randomized. Counts and percentage of patients with each type of deviation will be provided. Denominators for percentages will be the total number of patients randomized into each treatment arm or overall.

All protocol deviations will be presented in a data listing.

### **5.2. Demographics and Baseline Characteristics**

The demographic characteristics consist of age (years), age categories, sex, race, and ethnicity. The patient's age in years is recorded at screening. Age will be categorized as follows: 18 to <25, 25 to <35 years, 35 to <45 years, 45 to <55 years, and  $\geq 55$ , and <40 years and,  $\geq 40$  years. Race categories will be reported as White, Black, Asian, Hispanic and Other. The baseline characteristics consist of baseline height, baseline weight, and baseline body mass index (BMI) ( $\text{kg}/\text{m}^2$ ). Body mass index is calculated as body weight in kilograms/(height in meters).

A summary of demographics and baseline information will be presented for the ITT, ssITT, and PP Sets. Patients will be counted in the treatment arm to which they were randomized. All continuous data will be summarized using descriptive statistics. Counts and percentage of patients for will be provided for all categorical data. Denominators for percentages will be the total number of patients randomized into each treatment arm or who received topiramate + BOTOX.

All patient demographics and baseline characteristics will be presented in a data listing.

### **5.3. General Medical History**

Medical history will be coded using the Medical Dictionary for Regulatory Activities (MedDRA). The Safety Set will be used to summarize medical history overall (patients with any medical history) and for each system organ class (SOC) and preferred term (PT). Patients will be counted in the treatment arm to which they were randomized. Counts and percentage of patients

with each type of SOC and PT will be provided. Denominators for percentages will be the total number of patients randomized into each treatment arm, overall.

All patient medical history data including specific details will be presented in a listing.

#### **5.4. Inclusion and Exclusion Criteria**

The inclusion/exclusion criteria can be found in Section 4.3 and Section 4.4 of the protocol. A listing of patients not satisfying all inclusion/exclusion criteria will be presented in a listing. Inclusion/exclusion exemption along with the reason for the exception will also be presented in this listing.

## **6. Prior and Concomitant Treatments**

A prior treatment is defined as any treatment that is started prior to the first dose of study drug. A concomitant treatment is defined as any treatment that has a start date and a stop date that is on or after the date of first dose of study drug. Treatments with start and stop dates that bracket the first dose date will be summarized as both a prior and concomitant treatment.

All treatments being taken by the patients upon entry into the study or at any time during the study (in addition to the investigational product) are regarded as concomitant treatments and must be documented on the appropriate section of the eCRF. Prior and concomitant medications will be coded using the World Health Organization (WHO) drug dictionary. The total number of concomitant medications and procedures and the number and percentages of patients with at least one concomitant medication will be summarized by treatment arm. The number and percentages of all concomitant medications will be summarized by treatment arm and listed by drug class and preferred term and will be flagged as prophylactic or acute headache medications, if applicable. All summaries will be performed using the Safety Set. Patients will be counted in the arm in which they received treatment. Denominators for percentages will be the total number of patients treated in each treatment arm and overall.

All prior and concomitant medications as well as concomitant non-drug therapies, surgeries, and procedures will be presented in listings.

## **7. Study Treatment**

### **7.1. Duration of Exposure**

Duration of exposure is defined as the total number of days a patient is exposed to any study drug. For topiramate it will be presented as the total number of days from the first dose date (Day 1) to the last dose date (date of last dose minus the date of first dose + 1) as recorded on the End of Study/Early Withdrawal page on the eCRF. If the last dose date on the End of

Study/Early Withdrawal page is missing, or if a patient is lost to follow-up, but the eDiary confirms that the patient has taken study drug, the visit date following the last completed eDiary entry will be used. For BOTOX the duration of exposure will be defined as the total number of days from the first injection date (Day 1) to the last injection date plus 84 days (date of last dose + 84 days minus the date of first dose + 1) as recorded in the eCRF.

The duration of study drug exposure will be summarized for the Safety Set. Patients will be counted in the treatment arm for which they received treatment. Denominators for percentages will be the total number of patients treated in each arm.

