3.4 Schedule for Data Collection

Office visit data (ie, non-diary data) for this study will be collected using electronic case report forms (eCRFs) or eCOA at the screening visit, the day 1 (randomization/treatment) visit, and at 12-week intervals thereafter, coinciding with each office visit. Patient diary data will be collected daily via an e-diary during the 28-day run-in period and daily throughout the duration of the study. Patient-reported and clinician-reported outcomes will be collected via an eCOA. Follow-up data will be collected up to week 48, or up to 12 weeks after the last BOTOX injection.

4. Study Population and Entry Criteria

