6.5 Summary of Methods of Data Collection

An IWRS will be used to randomize patients and manage study medication inventory. All office visit data (ie, non-diary data) for this study will be collected using eCRFs via an electronic data capture system. Source documents will be used at the sites and may include a patient's medical record, hospital charts, clinic charts, the investigator's patient study files, as well as the results of diagnostic tests such as laboratory tests, X-rays, etc. A centralized clinical laboratory will be used for the analysis of all blood samples. Additional information on the collection and handling of samples is detailed in the Lab Procedure Manual.

Data required for the evaluation of the primary and some secondary efficacy measures will be recorded by patients using a daily e-diary. Patients will be asked to report data at approximately the same time each day, preferably at the beginning and end of the day, during the 28-day baseline period and throughout the study duration. The following data will be collected with the e-diary (patient instructions and training for completion of the e-diary will be provided):

- Estimated total duration of all headache(s) that day (if no headache, patient will report 0 hours)
- Maximum severity of headache(s) that day (mild, moderate or severe) (only for patients who report a headache duration of > 0)
- Any acute headache pain medication(s) used that day
- The dose of topiramate taken that day (only for patients receiving topiramate)
- MIBS-4 (only for patients who report a headache duration of 0)

Questionnaire data required to be directly collected from patients will be obtained at protocol-specified study visits using an electronic device. Questionnaires are to be completed by the patient and the answers to the questions on the questionnaires should come from the patients directly, not from family, friends, or the study support personnel. The patient may elect not to answer some or all of the questions. The patient questionnaires for a specific study visit should only be completed at that specific study visit. The patient will not have access to previously completed questionnaires.

Questionnaire data required to be directly collected from clinicians will be obtained at protocol-specified office visits and recorded on the eCOA.

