7.2.3.1 Imputation for Missing Values and Scoring Algorithms

For validated questionnaires, scoring will follow the guidelines set forth by the instrument developers and missing data handled per developer instructions. Imputation methods for missing values and scoring algorithms for other outcome measures will be detailed in the SAP.

Over the course of active treatment, each patient receiving topiramate will record the total daily dose taken in the e-diary system. If a patient skips a dose(s) or fails to take the specific maintenance dosing regimen, the patient will still be able to continue in the study.

Topiramate dosing compliance will be calculated based on the e-dairy data and if necessary, corresponding pill counts (number of pills actually taken, number of pills retrieved/returned, and the number of pills expected to have been taken by the patient while in the topiramate arm of the study). Topiramate dosing compliance details will be provided in the SAP. If the patient indicates that no topiramate treatment was taken in the e-dairy system and treatment discontinuation is reported at the subsequent office visit, then date of last dose taken will be the reported as date of discontinuation.

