## 7.2. Treatment Compliance and Modifications

Over the course of active treatment, each patient receiving topiramate will record the total daily dose taken in the eDiary system. If a patient skips a dose(s) or fails to take the specific maintenance dosing regimen, the patient will still be able to continue in the study.

Topiramate treatment compliance will be calculated based on the e-dairy data and if necessary, corresponding pill counts (number of pills actually taken, number of pills retrieved/returned, and the number of pills expected to have been taken by the patient while in the topiramate arm of the study). The overall topiramate compliance rate will be calculated by dividing the total mg of topiramate taken after Week 12 visit by the total mg of topiramate prescribed for all visits after Week 12 visit based upon the duration in the study and then multiplying by 100. The total mg of topiramate prescribed will be based on the maintenance dose set during the Week 12 visit.

The BOTOX compliance rate per visit will be calculated by choosing the minimum of the total units of BOTOX received at a visit divided by 155 U, the total number of injections sites divided by 31, 0.90 if a patient is +/- 8 to 10 days from the visit schedule or 0.80 if a patient is +/- 11 to 14 days from the visit schedule. This minimum value will then be multiplied by 100%. A patient that is 15 or more days from the visit schedule will result in a 0% for compliance (Table 3). The visit schedule is Day 1, Day 84 and Day 168. Overall BOTOX compliance will be the average of the total compliance from each visit.

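### The SAP's fallback end date for topiramate exposure is a visit date rather than a dosing date, and it can be late or undefined

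*SAP*

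**What the plan says.** SAP 7.1 first states the concept: "Duration of exposure is defined as the total number of days a patient is exposed to any study drug". For topiramate this is last dose date minus first dose date plus 1, with the last dose date read from the End of Study/Early Withdrawal page of the eCRF.

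The fallback has two triggers: that date is missing, "or if a patient is lost to follow-up, but the eDiary confirms that the patient has taken study drug". In either case "the visit date following the last completed eDiary entry will be used". The section does not say whether a home eCOA counts as a visit, or whether an actual or a scheduled visit is meant.

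Other text that bears on the rule:

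- SAP 7.2 states that "each patient receiving topiramate will record the total daily dose taken in the eDiary system". Protocol 6.5 lists the same daily item.
- Protocol 3.4 places office data collection at screening, Day 1 and "at 12-week intervals thereafter, coinciding with each office visit". SAP Table 1 gives target Days 1, 85, 169, 253 and 337 for the office visits. The same column lists the home eCOA weeks, with targets at Days 43, 127, 211 and 295.
- Protocol 8.5 asks a patient who stops topiramate to go on completing the diary.
- Protocol 7.2.3.1 covers a patient whose diary shows no topiramate taken and who reports discontinuation at the next office visit: "date of last dose taken will be the reported as date of discontinuation". SAP 7.2 has a similar rule for compliance below 80% or above 120%, taking the last treatment date from the eCRF or the eDiary.

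**The concern.** The fallback departs from the section's own definition. It applies only when the eDiary confirms dosing, so a dated dose should already be in the database when it is used. The rule passes over that date and takes a later visit, on which nothing shows that drug was taken.

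The second trigger adds two problems. A patient lost to follow-up may have no later visit, and the rule then yields no date. Also, the two triggers are joined by an or, so the fallback displaces a valid eCRF last dose date whenever the patient is lost to follow-up.

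At stake is the accuracy of the topiramate exposure summary in patients with incomplete records, and its agreement with discontinuation dates derived elsewhere.

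**Working it through.** The documents state no exposure figure, so there is none to reproduce. The check is date arithmetic on the SAP Table 1 target days, with the first dose on Day 1.

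**Formula.** Let L be the day of the last diary-recorded topiramate dose, E the day of the last completed diary entry, and V the day of the next visit after E.

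- Exposure to the last recorded dose: L − 1 + 1 = L days.
- Exposure under the fallback: V − 1 + 1 = V days.
- Excess: V − L = (V − E) + (E − L).

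The first term is the wait for the next visit. The second is diary-keeping after the drug was stopped.

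**Diary ends with dosing (E = L), office visits only.**

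- L = 84: 85 − 84 = 1 day.
- L = 100: 169 − 100 = 69 days.
- L = 86: 169 − 86 = 83 days.
- L = 1: 85 − 1 = 84 days.
- Range 1 to 84. If L is equally likely on any day from 1 to 252 (assumed), the mean is (1 + 84)/2 = 42.5 days.

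**Diary ends with dosing, home eCOAs counted as visits.**

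- L = 100: 127 − 100 = 27 days.
- Range 1 to 42; mean (1 + 42)/2 = 21.5 days on the same assumption.

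**Visits off target.** The documents give ±7 days for BOTOX sessions. If topiramate office visits move as much (assumed), a Week 12 visit on Day 78 and a Week 24 visit on Day 176 are 176 − 78 = 98 days apart.

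**Drug stopped, diary continued (E > L), eCRF date missing.**

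- L = 8, E = 252, V = 253: 253 − 8 = 245 days.
- L = 8, E = 336, V = 337: 337 − 8 = 329 days.

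These two cases disappear if the entry in question is read as the last entry recording a dose, but the SAP does not say so.

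**No visit after E.** V does not exist and exposure is undefined.

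**Arm mean.** The shift is the share using the fallback times the mean excess. The share is not in the documents; I assume 2% to 20%.

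- Office visits only: 0.02 × 42.5 = 0.85 days to 0.20 × 42.5 = 8.5 days.
- eCOAs counted: 0.02 × 21.5 = 0.43 days to 0.20 × 21.5 = 4.3 days.

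The planned topiramate period is up to 36 × 7 = 252 days. These shifts leave out patients with no later visit and those who kept the diary after stopping.

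**What else uses the date.** In the visible text, nothing beyond the Safety Set exposure summary:

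- SAP 9 and 9.1.1 divide adverse event counts by numbers of patients.
- SAP 9 divides topiramate from BOTOX safety data at the first BOTOX dose, and SAP 9.1 closes the treatment-emergent window at an office visit.
- SAP 5 counts patients who discontinued.
- Topiramate compliance in SAP 7.2 uses milligrams prescribed over time in the study.
- SAP 8 groups patients as randomized.

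**The case against.** The strongest defence is that the true last dose is unknown in these patients. Protocol 5.1 provides a 13-week supply, and Protocol 5.4.2.2 recommends a taper of up to 2 weeks, so a patient may dose after the last entry. The last recorded dose is then a lower bound and the next visit a late-date convention. This stands: the excess calculated here is over the last recorded dose, and the true excess may be smaller. It does not justify making the late date the main estimate when a recorded dosing date exists.

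A second defence is that large gaps should be rare. Under Protocol 7.2 a diary kept as instructed ends the day before the office visit, a gap of 1 day. A long gap from an abandoned diary requires that the patient later attended and the last dose date was still not recorded. Protocol 8.8 requires a discontinuation form, though it asks for the reason rather than the date. This limits the likely size but does not repair the rule.

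A reader might take 12 weeks as a ceiling on the error. It is only the scheduled gap between office visits; the documents also allow readings that give less or more.

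A reader might also infer that exposure and discontinuation dates must conflict. They need not. The rules in Protocol 7.2.3.1 and SAP 7.2 have different triggers from the fallback, and a patient can meet both only in some cases, for example when the eCRF date is blank.

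**Conclusion.** The point holds as a minor defect in a derivation rule. The fallback date is not a dosing date, is undefined for some of the patients it names, and can exceed the last recorded dose by up to about 42 days (eCOAs counted), 84 days (scheduled office visits), or more than 200 days (diary kept after an early stop). On the assumed 2% to 20% share, a uniformly distributed last entry and a diary that ends with dosing, the arm mean rises by about 0.4 to 8.5 days across the two readings of a visit.

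A reader might go further and infer that the rule makes topiramate look better tolerated or lowers its event rates. The documents do not support that. Protocol 2.2 judges tolerability by rates of adverse events and of discontinuations due to them. The visible SAP reports these as patient counts and percentages, plans no exposure-adjusted rate, and excludes hypothesis tests on safety results. The primary and secondary efficacy tests and the sample size are untouched.

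**What to change.** Reword the fallback in SAP 7.1 on these lines:

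- Use the eCRF last dose date whenever it is present, including for patients lost to follow-up.
- When it is missing, end topiramate exposure at the last eDiary day with a recorded topiramate dose above 0 mg. This agrees with the last-dose principle in Protocol 7.2.3.1 and the sources accepted in SAP 7.2.
- If wanted, report the next-visit date as an upper-bound sensitivity, stating whether eCOAs count as visits and what date applies when no later visit took place.

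The change is a sentence or two and uses data already collected; SAP 7.2 already plans a listing of topiramate accountability from the eDiary. The downside is slight understatement for a patient who went on dosing after the last diary entry, which the sensitivity would show.
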